The impact study design is a pragmatic, multi-site, effectiveness trial, with parent-infant dyads allocated to intervention and control within sites, at random, on a 1:1 basis. As a result, dyads are randomised within sites, which are local authorities, and the resulting data are clustered by site. Outcomes are recorded for the focal parent and focal child within dyads. There are four sites in total, with family dyads identified within each site by local intervention coordinators and then randomised to treatment and control using a randomised permuted block approach described more fully below.

Trained social workers are responsible, after training and discussions with Babies 1st, for identifying all eligible dyads that meet the inclusion criteria (with the exception of those for whom exclusion criteria apply), completing a referral form for each dyad and administering consent procedures. The referral form contains the following information:

- Focal parent’s contact details
- Focal parent’s age
- Focal child’s age
- Focal child’s gender
- Focal child subject to formal multi-disciplinary planning process (i.e. CP, CiN, Early Help Plan)?
- Other children in the household subject to formal multi-disciplinary plan?
- Ethnicity
- Focal parent’s care history
- Focal parent has other children taken into care?
- Does the focal parent smoke?

- Current accommodation
- Age focal parent finished full-time education
- Focal parent currently suffers from anxiety
- Focal parent currently suffers from depression
- Focal parent's alcohol consumption

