In line with WWCSA analytical guidance⁶, we will estimate the average effect of intention-to-treat (AITT) at the dyad (family) level using a two-sided test for statistical significance. We will obtain sample estimates of AITT via regression adjustment including an outcome measure derived from the baseline questionnaire as a covariate along with site fixed effects. The sample estimate of AITT will be converted from a regression coefficient into an effect size consistent with Glass's Delta for continuous outcomes. For binary outcomes, incident rates will be reported.

The table below presents the Minimum Detectable Effect Size (MDES) that the sample described is capable of detecting at the 95 per cent level of statistical significance and 80 per power. These calculations are considered to be provisional. They are made subject to an assessment of the degree of compliance with the intervention among the intervention group dyads. This assessment will be made at the Evaluation Review Point, which is discussed in more detail below. Should the assessment suggest that the assumptions made in these calculations are inaccurate, a revised protocol with updated calculations will be issued, with

⁶ What Works for Children's Social Care (2021). 'What Works for Children's Social Care Randomised Controlled Trial Statistical Analysis Guidance.'
<https://whatworks-csc.org.uk/wp-content/uploads/WWCSA-RCT-Statistical-Analysis-Guidance-V1.1-1.pdf>

further corrective actions take where necessary and possible within the general constraints faced by the trial.

MDES calculations account for the variation in sample sizes across local authorities by incorporating an estimate of cluster size based on the harmonic mean⁷ for the completed cases sample. Calculations were based on the assumed proportion of the variance in the outcome accounted for by the covariates in the fixed effects estimator (R^2). To establish the correlation coefficient, we identified the test-retest reliability for the MORS-SF warmth scale (0.70)⁸. This was then used to calculate the R^2 as the basis for the MDES.

MDES (Proportion of a Standard Deviation)		0.44
Proportion of Variance in Outcome Explained by Covariates⁹ (R^2)	Child	n/a
	Family (focal parent)	0.50
	Social Worker	n/a
Intracluster Correlations Coefficient (ICCs)	Family	n/a
	Social Worker	n/a
	Team	n/a
Alpha		0.05
Power		0.8
One-Sided or Two-Sided?¹⁰		Two-sided
Level of Intervention Clustering		Site
Average Site Size (harmonic mean)		21

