The primary analysis will be conducted according to the principle of intention to treat (AITT), recognising the possibility that some dyads allocated to the intervention will remain unexposed to the intervention. There is also a possibility that some dyads allocated to control, through error or subversion, are exposed to VIG. Essentially the trial data are analysed consistent with the allocation dyads received at randomisation regardless of whether they then went on to be exposed to VIG. This situation is slightly complicated by the challenges of missing data both at baseline and/or follow-up. These features of the data effectively create the following distinctions in the trial data:

- **The referred sample as randomised** – this sample contains complete records from the referral forms for all dyads referred and randomised.
- **The baseline sample as randomised** – this sample is all those dyads referred and randomised and who supplied the required data at baseline.
- **The follow-up sample at analysis** – this sample is all those dyads referred and randomised and who supplied complete data at follow-up. *Note*, we assume for child protection outcomes, obtained from administrative case files, there are no missing data at follow-up.
- **The completed cases sample at analysis** – this sample is all those dyads referred, randomised and who supply the necessary responses to the baseline and follow-up, such that the primary analysis described below can be conducted; that is prior to imputation
- **The imputed sample at analysis** – imputation at analysis will take different forms depending on which of the co-primary outcomes is considered (a full discussion of missing data and imputation strategy is provided below). For the primary outcomes derived from the MORS-SF scale the imputed sample at analysis contains all dyads referred and randomised, with either their observed values derived from the relevant items in the baseline and follow-up questionnaires, or where missing, their values on the relevant items required for the primary analysis filled-in using multiple imputation, should this prove a possible/viable strategy.

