The primary analysis involves obtaining a sample average treatment effect estimate. The analysis will be performed first on the *completed cases sample*, and then repeated on the *imputed sample at analysis* and *imputed sample at analysis – bounds*, in order to assess the likely consequences for the sample estimates of missing data. The average effect of intention to treat will be obtained on the basis of the following estimator¹⁶ for the warmth outcome (first co-primary outcome) derived from MORS-SF:

$$Y_{ij} = \sum_{j=k}^J \alpha_k S_{k,ij} + \beta_1 T_{ij} + \beta_2 X_{ij} + \varepsilon_{ij} \dots [1]$$

Where Y_{ij} is an observed value on the warmth scale derived from the MORS-SF instrument for dyad i at site $j = k$. This is a raw unstandardised value obtained from sample responses to the MORS-SF statements by focal parents, included in the follow-up questionnaire. The raw response values are preferred in order to maintain transparency and interpretability, and are derived by summing item scores across the seven items corresponding to the warmth scale. The assumption is that the respondent is the focal parent. The variable $S_{k,ij}$ is a binary indicator set equal to ‘1’ for dyad i at site $j = k$, zero otherwise. The variable T_{ij} is also a binary indicator variable, set equal to ‘1’ where dyad i at site $j = k$ is randomised to the intervention, zero otherwise. The constant term is suppressed, which means that sample estimates of α_k are the mean outcomes of Y in the control group at each site. The variable X_{ij} is a raw, unstandardised value for the baseline measure of Y for dyad i at site $j = k$. The

¹⁵ What Works for Children’s Social Care (2021). ‘What Works for Children’s Social Care Randomised Controlled Trial Statistical Analysis Guidance.’ <https://whatworks-csc.org.uk/wp-content/uploads/WWCSC-RCT-Statistical-Analysis-Guidance-V1.1-1-1.pdf>

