Here we allow for the effects of the intervention to vary across sites through the inclusion of a treatment by site interaction term. This specification permits us to test whether imbalances between intervention and control groups by site resulting from attrition, should they emerge, affect our sample estimates. We propose to obtain a sample average estimate by taking a weighted average of the site specific effects obtained from this model as follows:

$$\hat{\beta}_{IToT} = \sum_{J=1}^J \frac{N_J}{N} \hat{\beta}_k$$

Where $\frac{N_J}{N}$ is the proportion of the total sample at site J . The standard distributional assumptions regarding ε_{ij} are made. A weighted average of the standard error will also be formed in a similar manner. Site specific standard errors will be obtained using bootstrap procedures based on 500 replications. Inference on $\hat{\beta}_{IToT}$ will be performed through constructing frequentist 95 percent confidence intervals.

The second form of sensitivity analysis for the two primary outcomes involves an extension to model [1] above. It is proposed to include a full range of covariates in an extended regression analysis. Alongside a baseline measure of the dependent variable and site specific dummy variables we propose to obtain a sample estimate of AITT from a regression equation including additional covariates capturing:

- focal parent's age,

- baby's age in months; and
- presence of a partner

This analysis will test the sensitivity of the results to the specification of the regression equation and choices made over the inclusion of various covariates.

Missing data and imputation

As previously mentioned, one major challenge for this study will be missing data at both baseline and follow-up for the first two of the three co-primary outcomes derived from survey questionnaires (as well as secondary outcomes). In other words, obtaining unbiased estimates of AITT from the estimator represented by equation [1] above will likely be compromised by both unit and item non-response where estimates are obtained from fitting the statistical model to the completed cases sample file.

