Secondary analysis will consist of two sets of distinct analysis: first the derivation of sample estimates of the average effect of intention to treat on (1) parental self-efficacy (Karitane Parenting Confidence Scale); (2) Parental stress (Parental Stress Scale); and (3) the step-up/CSC escalation binary indicator. Second, for the primary analyses discussed above, for both co-primary outcomes, sample estimates of complier average causal effects (CACEs) will be obtained if it has proved possible to collect accurate take-up measures for individual dyads

Sample estimates of AITT for self-efficacy and parents stress will be obtained from fitting regression models to the relevant data consistent with the Equation [1] above, and using the same statistical procedures, where the dependent variables 'Y' and covariate 'X' are derived from the relevant scales and questionnaire data at baseline and follow-up. All model estimates will be derived from the completed cases sample files for the relevant data items.

A sample estimate of AITT for the step-up binary outcome will also be obtained as part of the secondary analysis. Sample estimates will be obtained from a linear probability model containing the following covariates, where the binary response is the dependent variable:

- Focal parent's age at randomisation (from the referral form)
- Focal baby's age in months at randomisation (from the referral form)
- Whether the father is present in the family home at randomisation (from the referral form)

The analysis will be performed on sample cases for those dyads randomised between July and November 2021. We anticipate that this sample will comprise some 150 cases. This analysis should not be affected by missingness. For binary outcomes, effect sizes will be reported as differences in adjusted incident rates.

If possible we will seek to obtain records on programme exposure for each dyad, whether allocated to intervention or control. If such indicators are of sufficient reliability and quality we propose to obtain complier average causal effects on the co-primary outcomes (Glennester & Takavarasha, 2013).

Exploratory Analysis

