Appendix A: Scales used in baseline and follow-up questionnaires

MORS-SF

1. My baby smiles at me
2. My baby annoys me
3. My baby likes doing things with me
4. My baby 'talks' to me
5. My baby irritates me
6. My baby likes me
7. My baby wants too much attention
8. My baby laughs
9. My baby gets moody
10. My baby dominates me
11. My baby likes to please me
12. My baby cries for no obvious reason
13. My baby is affectionate towards me
14. My baby winds me up

Warmth items: 1, 3, 4, 6, 8, 11, 13

Invasion items: 2, 5, 7, 9, 10, 12, 14

Scoring: 5 = Always; 4 = Very often; 3 = Quite often; 2 = Sometimes; 1 = Rarely; 0 = Never. No reverse scoring. Item scores are summed.

Karitane Parenting Confidence Scale

1. I am confident about feeding my baby
2. I can settle my baby
3. I am confident about helping my baby to establish a good sleep routine.
4. I know what to do when my baby cries
5. I understand what my baby is trying to tell me
6. I can soothe my baby when he/she is distressed
7. I am confident about playing my baby
8. If my baby has a common cold or slight fever, I am confident about handling this.
9. I feel sure that my partner will be there for me when I need support.
10. I am confident that my baby is doing well
11. I can make decisions about the care of the baby.
12. Being a mother/father is very stressful for me.
13. I feel I am doing a good job as a mother/father
14. Other people think I am doing a good job as mother/father
15. I feel sure that people will be there for me when I need support

Scoring: 3 = Yes, most of the time; 2 = Yes, some of the time; 1 = No, not very often; 0 = No, hardly ever. No reverse scoring. Item scores are summed.

Parental Stress Scale

1. I am happy in my role as a parent.
2. There is little or nothing I wouldn't do for my child(ren) if it was necessary.
3. Caring for my child(ren) sometimes takes more time and energy than I have to give.

4. I sometimes worry whether I am doing enough for my child(ren).
5. I feel close to my child(ren).
6. I enjoy spending time with my child(ren).
7. My child(ren) is an important source of affection for me.
8. Having child(ren) gives me a more certain and optimistic view for the future.
9. The major source of stress in my life is my child(ren).
10. Having child(ren) leaves little time and flexibility in my life.
11. Having child(ren) has been a financial burden.
12. It is difficult to balance different responsibilities because of my child(ren).

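### Baby's age is collected before randomisation but left out of primary model [1]; adding it is a nearly free refinement for the warmth outcome, of unknown size

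*Protocol*

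**What the plan says.** All references are to the protocol.

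- **Collection.** The Design section lists "Focal child’s age" among the referral-form items, which are gathered before randomisation. The Analysis Plan says of the referred sample that "this sample contains complete records from the referral forms for all dyads referred and randomised".
- **Primary model.** The sample size section describes the regression as "including an outcome measure derived from the baseline questionnaire as a covariate along with site fixed effects". In the Primary Analysis section, equation [1] contains site indicators, the treatment indicator and one further covariate, X, which "is a raw, unstandardised value for the baseline measure of" the same outcome. Invasion is analysed in the same way as warmth.
- **Where age does appear.** The second sensitivity analysis of the primary outcomes adds three covariates together: the focal parent's age, "baby's age in months; and" presence of a partner. Its purpose is given as: "This analysis will test the sensitivity of the results to the specification of the regression equation and choices made over the inclusion of various covariates". The Secondary Analysis section also adjusts the step-up model for the baby's "age in months at randomisation (from the referral form").
- **Population and stratification.** The focal child is 12 months old or younger, and randomisation is stratified by site only.
- **Instrument.** Appendix A gives seven warmth items, among them "My baby smiles at me", and seven invasion items.

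**The concern.** Three of the seven warmth items ask whether the baby smiles, 'talks' or laughs. What a parent can report on these plausibly differs between a newborn and an older infant. Two babies with the same low baseline warmth score may therefore have different expected scores at follow-up: one may be too young to show the behaviour yet, while the other is old enough to show it. If so, age carries information about follow-up warmth that the baseline score does not.

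What is at stake is precision. A covariate that is measured before randomisation, recorded for everyone and predictive of the outcome narrows the confidence interval at negligible cost. As planned, the interval reported as primary does not use it.

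**Working it through.** **Inputs from the protocol.** Two-sided alpha 0.05; power 0.80; 1:1 allocation; R² = 0.50 (from a test-retest correlation of 0.70, squared 0.49); four sites; harmonic mean site size 21; 141 complete cases; printed MDES 0.44. **Input not in the protocol:** p, the share of the variance remaining after baseline score and site that age explains. It is assumed here.

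**Step 1: reproduce the printed MDES.** MDES = M × sqrt((1 − R²) / (0.25 × N)), where M = t(0.975) + t(0.80) on N − 6 degrees of freedom (four sites, treatment, baseline score).

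- N = 4 × 21 = 84, 78 df: M = 2.837 and sqrt(0.50/21) = 0.1543, so MDES = 0.438, which rounds to the printed 0.44.
- N = 141, 135 df: M = 2.822 and sqrt(0.50/35.25) = 0.1191, so MDES = 0.336.

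Both bases are carried forward. The proportional effect of adding age is essentially the same on either. Why the table prints 141 cases beside a figure that matches 84 is a separate question.

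**Step 2: add age.** R² becomes 0.50 + 0.50p, the SE is multiplied by sqrt(1 − p), one further degree of freedom is used, and the equivalent number of complete cases is 141/(1 − p).

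| p (assumed) | SE falls by | MDES, N = 84 | MDES, N = 141 | Extra complete cases on 141 |
|---|---|---|---|---|
| 0 | 0% | 0.438 | 0.336 | 0 |
| 0.01 | 0.5% | 0.436 | 0.334 | about 1 |
| 0.05 | 2.5% | 0.427 | 0.328 | about 7 |
| 0.10 | 5.1% | 0.415 | 0.319 | about 16 |
| 0.15 | 7.8% | 0.404 | 0.310 | about 25 |

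**Step 3: is 0-15% a sensible range?** The baseline score already absorbs part of any age effect, so what matters is what age adds beyond it. Let r = 0.70 be the correlation between baseline and follow-up, a that between age and baseline, and b that between age and follow-up. Then p = (b − ra)² / ((1 − r²)(1 − a²)). The values of a and b below are illustrative; the protocol gives neither.

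- a = 0.4, b = 0.3: p = (0.02)² / (0.51 × 0.84) = 0.001, so the SE is unchanged.
- a = 0.2, b = 0.3: p = (0.16)² / (0.51 × 0.96) = 0.052, so the SE falls 2.6%.
- a = 0.4, b = 0.1: p = (0.18)² / (0.51 × 0.84) = 0.076, so the SE falls 3.9%.
- a = 0.4, b = 0: p = (0.28)² / (0.51 × 0.84) = 0.183, so the SE falls 9.6%.

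Plausible patterns thus run from no gain to a little under 10% of the SE. The 0-15% range for p is a working range, not a bound.

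**Step 4: cost if age explains nothing.** One degree of freedom out of 135 is about 1/135 = 0.7% of the variance, or under 0.4% of the SE.

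**Step 5: chance imbalance.** The standardised difference in mean age between arms has SD 2/sqrt(141) = 0.17. With p = 0.05 to 0.15, a one-SD imbalance moves the estimate by sqrt(0.50p) × 0.17, or about 0.03 to 0.05 outcome SD. Model [1]'s standard error already includes this variation, so it is the same benefit as in step 2 and not a second one.

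**The case against.** The case for leaving the plan alone is substantial. Model [1] is a valid intention-to-treat estimator. It adjusts for the baseline value of the same scale, which the protocol expects to be the most influential covariate. No statement or figure is contradicted, and the MDES of 0.44 does not rely on age. An age-adjusted estimate is already pre-specified as a sensitivity analysis, and referral-form covariates feed the multiple imputation model. All of that stands. It does not fully answer the point, because the sensitivity model enters age only together with two other covariates and leaves the primary interval as it is.

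A reader might infer more than the protocol supports:

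- **That age drives MORS-SF scores, so leaving it out wastes precision.** The protocol has no figure on how scores vary with infant age, and the gain may be nil. Smiling, 'talking' and laughing are three of seven warmth items and none of the seven invasion items.
- **That omission biases the result.** Leaving out a baseline covariate does not bias a randomised linear comparison. The protocol does expect follow-up missingness to differ by arm, but nothing in it says that response depends on the baby's age, so age adjustment cannot be presented as a cure for attrition.
- **That adjusting the step-up model for age but not model [1] is inconsistent.** The step-up model lists no baseline score, so demographic covariates are all that it has. The MORS-SF models do have one.

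**Conclusion.** The point holds as an optional improvement, centred on warmth. The facts are firm: age is collected before randomisation, is described as complete, and is absent from model [1]. The size of the benefit is not firm. On an assumed 0-15% of residual variance, the SE falls by 0-8%, worth between 0 and about 25 complete cases on 141. This rests on the protocol's R² of 0.50 and on an age effect that the protocol does not quantify. For invasion, the reason to add age is that both co-primaries should use the same model; item content does not support it. The current plan is valid and nothing in it needs correcting.

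**What to change.** In model [1], add the baby's age in months at randomisation, taken from the referral form, as a pre-specified linear covariate for warmth. Do the same for invasion so that the two co-primary models match. Keep the present model without age as a sensitivity analysis. Doing the same in the Karitane and Parental Stress models is optional, and the item-content argument does not support it.

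The cost is one degree of freedom per model and a line of text, with no new data and, if referral records are complete as described, no lost cases. The change should be fixed before any outcome data are analysed; the evaluation review point planned for September 2021 already allows for protocol changes.

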Once referral and consent procedures are complete, details of each dyad are passed to IFF Research, who check the completeness of the referral form data and confirm eligibility (that the dyad meets the study inclusion criteria). Subsequently, IFF administer a baseline questionnaire to the focal parent. The baseline questionnaire contains the following measures, details of which can be found in Appendix A: MORS-SF, Karitane Parenting Confidence Scale, Parental Stress Scale. For the sample randomised between July and November 2021, child protection outcomes (CiN, CPP, CLA and initiation of pre-proceedings) are collected from administrative case data held by the local authorities and further details provided later in this section. Full details of the measures included within the baseline questionnaire, along with the justification for their choice, and the reliance on self-completion questions rather than observations, is provided in the section entitled 'Outcome measures' below.

The respondent (focal parent) is expected to be the focal child's mother but may be the father where he is the only, or primary, care giver. Dyads are given two weeks to complete the questionnaire. It is important to note, that the study's funders have decided that all dyads that meet the study inclusion criteria and who provide their consent should be randomised, regardless of whether a complete baseline questionnaire is received. This means that some missing data, either item or unit (dyad) missing, can be expected at baseline. The evaluators in partnership with Babies 1st and the study sites will take a number of steps to limit non-response or missingness at baseline, such as telephone reminders to non-respondents, telephone support for focal parents to complete the questionnaire, and support for social workers and VIG Practitioners to support and encourage parents to participate.

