Once the period of time given to dyads to complete the baseline questionnaire has elapsed, IFF Research link the questionnaire return to the dyad's referral form data, pseudonymise the data and pass the data record to Manchester Metropolitan University (Man Met). A researcher based in Man Met's Policy Evaluation and Research Unit (PERU), who is blind to the identities of the dyads concerned will then randomise that dyad. Full details of the randomisation procedures are set out below. Once the dyad has been randomised, the outcome of randomisation is communicated by Man Met to IFF Research who in turn inform the Local Authority (LA) of the outcome. Following randomisation, LAs are free to commence work with dyads allocated to the intervention. It is expected that LAs will commence work with dyads very soon after randomisation so that the time between the end of the intervention and collection of post-intervention data is consistent across dyads. LAs should therefore only refer dyads for whom intervention delivery could commence immediately.

IFF Research will administer a follow-up questionnaire to all dyads (including those that did not supply a baseline questionnaire) five months following randomisation. Dyads will be given two weeks to complete the follow-up questionnaire. In large part, the follow-up questionnaire will contain the same or similar questions as the baseline questionnaire, and a similar set of procedures will be followed in order to limit attrition and missingness. IFF Research will seek a complete follow-up questionnaire from all randomised dyads, regardless of whether a dyad completed a baseline questionnaire.

At the end of the 'follow-up' fieldwork period, IFF Research will pseudonymise the follow-up questionnaire data and pass them to Manchester Met for analysis. Full details of the analysis are discussed below.

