Sample Size	Intervention	71
	Control	70
	Total	141

The sample size in the table above considers assumed missingness in the data, due to participants not completing a baseline questionnaire, a follow-up questionnaire, or both). We have assumed close to full compliance with the intervention; though as discussed previously this assumptions is subject to review. The calculations are illustrated in the following table:

⁷ Dong, N., & Maynard, R. A. (2013). 'PowerUp!: A tool for calculating minimum detectable effect sizes and minimum required sample sizes for experimental and quasi-experimental design studies.' *Journal of Research on Educational Effectiveness*, 6(1), 24-67.
doi: 10.1080/19345747.2012.673143.

⁸ Oates, J. and Gervai, J. (2019) 'Mothers' perceptions of their infants', *Journal of Prenatal and Perinatal Psychology and Health*, vol. 33, pp. 282-300.

⁹ This includes, and will most likely be most influenced by, a baseline measure of the outcome.

¹⁰ By default, we would recommend two-sided tests.

Table 3: Anticipated sample sizes at baseline and follow-up

	Recruited eligible dyads	As randomised sample	Baseline questionnaires obtained	Follow-up questionnaire (those not supplying a baseline response)	Follow-up questionnaire (those supplying a baseline response)
Achieving for Children	120	120	96	12	67
Stockport	84	84	67	8	47
BANES	24	24	19	2	13
London Borough of Hounslow	24	24	19	2	13
Total	252	252	202	25	141
Assumed response patterns					
Non-responder at both waves	25				
Responder at baseline missing at follow-up	60				
Missing at baseline responder at follow-up	25				
Responder at both waves	141				

Outcome Measures

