Our approach is to conduct the primary analyses for each of the co-primary outcomes identified, following the approach set out in the previous sections, on the completed cases sample at analysis. Then for the co-primary outcomes derived from the MORS-SF instrument, to sensitivity test the results from these analyses by assessing the likely consequences for sample estimates of missing data being MAR. Whilst MAR could in theory be addressed through adding the necessary covariates to the model implied by equation [1], the proposed strategy we adopt, that of Multiple Imputation, preserves sample size. We propose to fit an imputation model, using the data augmentation approach (based on cycles of imputation using the MCMA algorithm) and multivariate normal assumption in STATA v17 (using the mi impute suite of commands) where values for the primary outcome Y and covariate X are imputed on the basis of a model containing further covariates from the referral forms and possibly values of the other outcomes available at follow-up and baseline depending on patterns of missingness in these variables¹⁸. The burn-in phase for the imputation will consist of 500 imputation cycles with the number of imputed data sets set equal to the highest FMI (fraction of missing information) for either Y or X determined from an initial run, and with 100 cycles between the creation of each imputed data set. Imputation will be conducted in intervention and control groups separately. The stability of the imputation will be assessed through inspecting variance information and standard plots for Y and X . If these appear satisfactory, equation [1] will be estimated on the final merged

¹⁷ In the case where baseline covariate values only are missing, null or mean imputation methods are likely to work well in preserving power and unbiased AITT because the values of the coefficients on the X s are not in and of themselves of interest and they are uncorrelated with T in expectations (Puma et al., 2009)

¹⁸ There are arguments against the use of multiple imputation in randomised trials. Sullivan et al. (2018) show some loss of efficiency when compared to completed cases analysis with full regression adjustment but this result is obtained where data are missing on the outcome at follow-up only. We believe in the case of this study, multiple imputation if achievable, represents the most practical strategy open to us.

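### The primary, Karitane and PSS analyses leave out about 25 of 166 dyads with an observed follow-up outcome, solely because their baseline questionnaire is missing

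*Protocol*

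**What the plan says.** Under Design, eligible consenting dyads "should be randomised, regardless of whether a complete baseline questionnaire is received", and "IFF Research will seek a complete follow-up questionnaire from all randomised dyads, regardless of whether a dyad completed a baseline questionnaire". Table 3 has a row "Missing at baseline responder at follow-up" with 25 dyads, beside 141 who respond at both waves.

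The Analysis Plan defines several samples. For completed cases, "this sample is all those dyads referred, randomised and who supply the necessary responses to the baseline and follow-up". A separate follow-up sample, requiring complete follow-up data only, is also defined, but Primary Analysis does not list it among the samples to be used. The co-primary outcomes are analysed "following the approach set out in the previous sections, on the completed cases sample at analysis", then again on the multiply imputed and bounds samples. Secondary Analysis fits the Karitane and PSS models to completed cases.

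On missing baselines, the section Missing data and imputation says that dropping such dyads is unlikely to bias the estimate but reduces the sample. Footnote 17, for the case where only baseline covariates are missing, adds that "null or mean imputation methods are likely to work well in preserving power and unbiased AITT". Mean imputation with a missing-value indicator is specified, but only inside the extreme-bounds analysis.

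**The concern.** The trial decides to randomise dyads without a baseline form and pays to follow them up. It then leaves their observed outcomes out of the headline estimate because a covariate is absent. The protocol already holds a simple method for keeping them and speaks well of it.

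The stated target is the effect of offering VIG, by allocation as randomised. Completed cases describe baseline responders who also returned a follow-up. At stake are closeness to the randomised population and a modest amount of precision. For Karitane and PSS, the follow-up scores of these dyads would not be analysed as outcomes at all.

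**Working it through.** **Inputs.** From Table 3: 252 randomised, 202 with a baseline, 141 with both waves, 25 with follow-up only. From the sample size section: two-sided alpha 0.05, power 0.80, test-retest correlation 0.70 (squared 0.49, shown as 0.50). Allocation is 1:1. The R² values 0.60, 0.36 and 0.25 below are assumptions that show a range.

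**The plan's own figures.** 10% of 252 is 25.2 and 70% of 202 is 141.4, which gives the printed 25 and 141. The site entries add to 24 and 140, which is rounding. The MDES is M × sqrt((1−R²)/(0.25N)) with M = 1.960 + 0.842 = 2.802. The harmonic mean of 67, 47, 13 and 13 is 21.05. With N = 4 × 21 = 84 this gives 0.432 at R² = 0.50, 0.438 with t quantiles, and 0.442 with t quantiles and R² = 0.49. That is the printed 0.44. Putting N = 141 in directly gives 0.334. I compare before and after on the direct count, so that both sides share one basis.

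**Coverage.** 141/252 = 56%. (141 + 25)/252 = 166/252 = 66%. Share of observed outcomes left out: 25/166 = 15%.

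**Where the 25 dyads enter**
- Primary model, site-interaction model and extended-covariate model: no (completed cases).
- Multiple imputation: yes, together with imputed outcomes for others, and only if it proves viable.
- Fallback if multiple imputation performs poorly: no (extra covariates on completed cases).
- Extreme bounds: yes, together with extreme values for missing outcomes.
- Karitane and PSS models: no.

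**Variance of the effect** (outcome SD 1, arms balanced with and without a baseline, site terms ignored)
- Completed cases: 4(1−R²)/141
- All 166, mean imputation plus indicator, unweighted: 4[141(1−R²) + 25]/166²
- All 166, best weighting: 1/[141/(4(1−R²)) + 25/4]

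At R² = 0.50:
- Completed cases: 2/141 = 0.01418, SE 0.1191, MDES 0.334.
- Unweighted: 4 × 95.5/27,556 = 0.01386, SE 0.1177, MDES 0.330.
- Weighted: 1/(70.5 + 6.25) = 0.01303, SE 0.1141, MDES 0.320.

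Power at an effect of 0.334 goes from 80.0% to 80.9% unweighted or 83.2% weighted.

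Variance relative to completed cases:

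| R² | Unweighted | Weighted |
|---|---|---|
| 0.60 | 1.041 | 0.934 |
| 0.50 | 0.977 | 0.919 |
| 0.36 | 0.921 | 0.898 |
| 0.25 | 0.892 | 0.883 |

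**Break-even for the unweighted fit.** Setting 141[141u + 25] = 166²u, with u = 1−R², gives u = 3,525/(27,556 − 19,881) = 0.459, so R² = 0.54.

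**Simulation.** With 20,000 trials, baseline missing completely at random, R² = 0.50 and a true effect of 0.30, the mean estimate was 0.300 for completed cases and for the unweighted 166-dyad fit. Empirical SEs were 0.122 and 0.120 (ratio 0.98), in line with the formula.

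**Expected follow-up loss.** Baseline responders: 60/202 = 30%. Baseline non-responders: 25/50 = 50%.

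**The case against.** The best defence is that the choice is open and reasoned. The protocol states the loss, sizes the trial on 141, and commits to analyses that include these dyads; the bounds are unconditional. Footnote 17 covers the case where only the baseline is missing, and says likely, not certain. This trial also expects follow-up loss that may differ by arm, and the added dyads come from the group with the heavier loss and have no baseline score to adjust for it. At the planned R² the simple unweighted fix gains about 1% in SE, and it would lose precision if R² were somewhat higher. All of this stands and limits the weight of the point.

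A reader might infer more than the documents support:
- *That the headline estimate is biased.* Baseline missingness precedes randomisation, the protocol says bias from dropping these dyads is unlikely, and nothing shows otherwise.
- *That the least engaged families are excluded.* The protocol does not say this; the 25 expected to be missing at both waves respond less than these 25 do.
- *That much power is thrown away.* Treating all 166 as if they had R² = 0.50 would give an MDES of 0.308, but the added dyads carry no baseline information.
- *That the fix delivers the effect in everyone randomised.* 252 − 166 = 86 dyads (34%) still have no follow-up outcome.

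What the defence does not answer is that no planned analysis rests on the 166 observed outcomes without imputing others. If multiple imputation fails, these dyads inform no primary point estimate, only the bounds. For Karitane and PSS no imputation is specified at all.

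**Conclusion.** The point holds as a cheap improvement to the choice of analysis set, not as a demonstrated bias or a serious power loss. About 15% of observed follow-up outcomes are left out of the primary, Karitane and PSS estimates for want of a covariate. Including them raises coverage of randomised dyads by 10 percentage points. At R² = 0.50 it cuts variance by about 2% unweighted (SE about 1%) or about 8% weighted (SE about 4%). At an assumed R² of 0.36 or 0.25 the unweighted reduction is about 8% or 11%.

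These figures rest on Table 3's response pattern, on balanced arms, and on the test-retest correlation standing in for the baseline-to-follow-up correlation. Because the planned R² of 0.50 lies close to the break-even of 0.54, the gain is secure only if the fit allows for the larger residual variance of dyads without a baseline. The main threat the protocol names, loss at follow-up, is untouched.

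**What to change.** Make the already defined follow-up sample (about 166 dyads) the primary analysis set for both MORS-SF outcomes. In equation [1], set a missing baseline score to the overall mean and add a missing-baseline indicator, as the bounds analysis already does. Let the residual variance differ between dyads with and without a baseline, by a weighted fit or an equivalent model. Keep completed cases (141) as a sensitivity analysis, and apply the same rule to Karitane and PSS. The multiple imputation and bounds analyses stay as planned, since they address follow-up loss.

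State one trade-off in the text. At R² = 0.50, weighting gives the added dyads 25/(282 + 25) = 8% of the total weight (282 = 141/0.50), against 15% unweighted. If the effect differed by baseline completion, the two fits would therefore average it differently.

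The cost is a few sentences of protocol or SAP wording, one extra model term and a variance option. No further data are needed.
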